3.5.10 Discontinuation of Study Participants

Each subject is free to discontinue from the study at any time, for any reason, and without penalty or loss of benefit. Participation in the study treatment may be discontinued for any of the following reasons:

• Occurrence of any medical condition or circumstance that exposes the subject to substantial risk and/or does not allow the subject to adhere to the requirements of the protocol, including early removal of LYR-210

- Any serious AE (SAE, Section 7.2), clinically significant AE, severe laboratory abnormality, intercurrent illness, pregnancy, or other medical condition that indicates to the Investigator that continued participation is not in the best interest of the subject.
- Subject's decision to withdraw
- If deviations to the use of prohibited medications occur after randomization and study treatment, the Investigator in consultation with the Sponsor and Sponsor's medical monitor will decide on a case-by-case basis whether the subject may continue in the study based on the time the prohibited medication was administered and its pharmacology.
- Subject's failure to comply with protocol requirements or study related procedures.
- Termination of the study by the Sponsor or a regulatory authority that has provided approval to proceed.

Subjects who withdraw or are withdrawn from the study treatment will be requested to return to the clinic for the assessments and procedures scheduled for the end of treatment visit and the safety follow up visits (Section 3.5.9). The Investigator or study staff will document the reason(s) for subject discontinuation on the Case Report form (CRF) and notify the IRB/EC as required by their Institution's procedures.

3.6 Data collection

Study data will be collected according to good clinical practices (GCP). Data will be entered into the study database by investigational site staff using the data will be reviewed by Lyra Therapeutics staff, or designee, and any queries will be submitted to the investigational site for clarification. Patient-reported outcome questionnaires will be entered into an ePRO device (eg, electronic tablet), smartphone application, or computer URL directly by study participants.

3.7 Study assessments, endpoints, and activities

The study assessments are described below. Frequency of each assessment is found in the Schedule of Assessments (**Appendix 14.1**).

3.7.1 CRS Cardinal Symptoms ePRO

Enrolled participants will be asked to complete a daily ePRO questionnaire to assess the severity of the 4 individual cardinal symptoms of CRS (nasal blockage/obstruction/congestion, facial pain/pressure, anterior/posterior nasal discharge, and reduction/loss of smell). 7,8 Each symptom is scored on a 0-3 scale as follows: 0 = none, 1 = mild, 2 = moderate, and 3 = severe.

In addition, the 4CS ePRO will capture use of daily saline irrigation by the participants.

3.7.2 SNOT-22 questionnaire

The SNOT-22 questionnaire is a 22-item disease-specific quality of life instrument validated for use in CRS.¹¹ Each symptom is scored on a 6-point scale as follows: 0 = no problem, 1 = very mild problem, 2 = mild or slight problem, 3 = moderate problem, 4 = severe problem, 5 = moderate problem

problem as bad as it can be. The total SNOT-22 score is the sum of the 22 items and can range from 0 to 110 with higher scores indicating worse symptoms. The MCID for the total SNOT-22 score has been determined to be 8.9 units. Additionally, the SNOT-22 scores can be divided into subcategories of rhinologic symptoms, extra-nasal rhinologic symptoms, ear/facial symptoms, psychological dysfunction, and sleep dysfunction¹².

- 3.7.3 Patient Global Impression of Severity (PGIS) questionnaire
 Participants will be asked a single question to rate their severity of CRS-related symptoms over the past 7 days
- 3.7.4 Patient Global Impression of Change (PGIC) questionnaire
 The PGIC is a self-assessment of the participant's overall change in CRS-related symptom severity compared to pretreatment.
- 3.7.5 Work Productivity and Activity Impairment (WPAI-SHP) questionnaire
 The WPAI-SHP is a questionnaire to measure the effect of a specific health problem on the participant's work productivity and normal daily activities. ¹³ Employed participants report absenteeism, (time absent from work) and presenteeism (time at work but not fully productive), which are calculated to a work productivity index. All participants report time away from normal activities.
- 3.7.6 General quality of life questionnaires (SF-36v2, EQ-5D-5L)

[figure not shown]
 Participants will complete 2 general quality of life questionnaires, the SF-36v2 and EQ-5D-5L.

The SF-36v2 health survey captures participants' perceptions of their health and well-being in 8 dimensions: physical functioning, physical limitations, emotional limitations, social functioning, bodily pain, general health, and mental health. ¹⁴ The items of the SF-36v2 are transformed and summed to a norm-based scale (mean=50, SD=10) for each physical and mental component domain in which higher scores indicate a better health-related quality of life status.

The EQ-5D-5L descriptive system comprises the following 5 dimensions, each describing a different aspect of health: mobility, self-care, usual activities, pain/discomfort, and anxiety/depression. Each dimension has 5 response levels of severity: no problems, slight problems, moderate problems, severe problems, 'unable to'/extreme problems. In addition, the EQ-VAS records the overall current health on a vertical visual analogue scale, where the anchors are labelled 'the best health you can imagine' and 'the worst health you can imagine'.

3.7.7 Sleep questionnaire (MOS Sleep-R)

MOS Sleep-R is a 12-item instrument with a 4-week recall designed to measure key aspects of sleep, such as disturbance, adequacy, somnolence, and quantity. ¹⁶ The score ranges from 0 to 100, lower scores indicating better sleep and higher scores indicating worse sleep. The scale yields a sleep problem index and scores on the following 6 subscales: sleep disturbance, snoring, shortness of breath or headache, sleep adequacy, sleep somnolence, and sleep quantity.

3.7.11 Nasal endoscopy

Nasal endoscopies will be performed to evaluate presence/absence of and grade of nasal polyps and to document presence of epistaxis, mucosal erosion or ulceration, perforation, and any other local adverse effects. The endoscopic assessment of nasal polyps for eligibility will be conducted at Screening. A central reviewer will evaluate the screening endoscopy to determine presence/absence of polyps and polyp grading (see **Appendix 14.2** for the nasal polyp grading scale), if applicable. The central assessment will be used for randomization stratification. Participants are required to wear a blindfold and headphones during any endoscopy examination to maintain their blind to treatment assignment. All nasal endoscopies will be recorded and uploaded to the Central Imaging Core Lab repository. Nasal endoscopies will also be reviewed at the Central Imaging Core Lab for evaluation of presence of epistaxis, mucosal erosion or ulceration, perforation, and any other local adverse effects.

3.7.12 SCS rescue

Systemic corticosteroids (SCS) for rescue treatment of CRS or for another reason that are prescribed to the participant are to be recorded in the eCRF. If possible, an endoscopy should be performed before starting treatment with SCS. The participant should continue with the study treatment and follow-up visits per protocol. The investigator (or designee) will record the dates and dosing information (dosage form, daily dose, duration, name of drug) on the appropriate page(s) of the eCRF. Indication for SCS use will also be captured by selecting 1 or more of the following categories:

- 1, CRS
- 2. Asthma
- 3. Other respiratory or ENT disease (specify)
- 4. Other reason (specify).

A course of SCS is considered continuous if treatment is separated by less than 7 days.

3.7.13 Sinonasal surgery (actual or planned) for CRS

For participants who have a surgery or have a scheduled date for sinonasal surgery as rescue for CRS, the reason (worsening signs and/or symptoms during the study), the date the surgery was indicated, expected or actual surgery date, and the type and outcome of surgery will be recorded in the eCRF. Types of sinonasal surgery include, but are not limited to, functional endoscopic sinus surgery (FESS), balloon sinuplasty, turbinate reduction, septoplasty or polypectomy, or any endoscopic procedure that results in sinonasal tissue removal.

If the surgery is to be performed during the study treatment period, the study treatment will be discontinued and all procedures/assessments for the ET and EOTP visits will be completed prior to the surgery. The participant will be discontinued from the study.

If the surgery is to be performed during the safety extension phase, the study treatment will be discontinued and all procedures/assessments for the ET and EOSEP visits will be completed prior to the surgery. The participant will be discontinued from the study.

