3.5.8 End of treatment phase (Week 24)

All participants will undergo a Week 24 visit. If medically warranted per the treating physician's discretion (for example, needing sinonasal surgery as rescue treatment), early matrix removal

may be performed at an unscheduled **early treatment termination (ET)** visit. Any participant who undergoes an ET visit is required to complete the assessments scheduled for the Week 20/ET visit, and subsequently the Week 24/End of Treatment Phase (EOTP) visit within 25-31 days of the ET visit. ET participants are encouraged to continue completing ePRO assessments through Week 24.

Week 24/EOTP assessments include a urine pregnancy test for women of childbearing potential, COVID-19 test, hematology and chemistry tests, nasal endoscopy, ocular examination (IOP and slit lamp), all ePRO (4CS, SNOT-22, WPAI-SHP SF-36v2, EQ-5D-5L, PGIS, PGIC, MOS Sleep R), concomitant medications/procedures, nasal swab collection, and AEs.

Participants will also complete the End of Treatment (EOT) at this visit.

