The study treatment will be discontinued and all procedures/assessments for the ET and end of treatment phase (EOTP) visits will be completed prior to the surgery. The participant will be discontinued from the study.

The sinonasal surgery requirement through Week 24 is derived by checking whether the sinonasal surgery is indicated before Week 24, inclusive. If a participant is lost to follow up/discontinues the study before Week 24 and does not have sinonasal surgery requirement at that time, this will be considered as a missing data for the analysis.

3.1.4.10 Total systemic corticosteroid (SCS) dose prescribed through Week 24

SCS for rescue treatment of CRS or for another reason that are prescribed to the participant are to be recorded in the eCRF.

If possible, an endoscopy should be performed before starting treatment with SCS. The participant should continue with the study treatment and follow-up visits per protocol. The investigator (or designee) will record the dates and dosing information (dosage form, daily dose, duration, name of drug) on the appropriate page(s) of the eCRF. Indication for SCS use will also be captured by selecting 1 or more of the following categories:

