3.1.8.3 Missing data

All efforts will be made to minimize missing data. Participants who discontinued treatment early are encouraged to continue completing ePRO assessments through Week 24. Data collected after treatment discontinuation will be included in the analysis. For participants who undergo rescue treatment (SCS and/or sinonasal surgery for any reason), data collected post rescue treatment will be censored and imputed using the participant's worst possible.

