3.4.1.3 Supplementary Analysis

- The same MMRM model defined in the primary analysis will be performed based on the Per-Protocol Population

Additional sensitivity analyses (supplementary estimands) will be conducted by the following alterations of the primary estimand regarding the handling of intercurrent event of SCS use or ESS while keeping the same strategy as the primary estimand for the other intercurrent events.

- 1) Supplementary 1: Treatment policy strategy for the use of SCS for any indication or ESS
- 2) Supplementary 2: Composite strategy of participant's worst post-baseline value for SCS for CRS indication and ESS; Treatment policy for SCS use for other indication.

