Appendix C

List of Changes in SAP Version 2.0 from Version 1.0

SAP Sections	Description	Rationale
3.4.1.1	Stratum Nasal Polyp is removed from the primary analysis model MMRM	Remove as the primary analysis population is the participants without nasal polyp.
3.4.3.1	Added sensitivity analysis with a treatment policy for ICE of SCS use and ESS	To incorporate treatment policy in consideration of FDA's feedback.
3.4.3.1	Added sensitivity analysis of composite strategy for ICE of SCS use and ESS for CRS indication and a treatment policy for SCS use for non-CRS indication.	To assess robustness of the primary estimand.
3.6.1	Added definition of treatment emergent AESI. Added summary measures for AESI and AEs leading to discontinuation, ie risk difference between the treatment groups and its 95% CI.	To incorporate FDA's feedback.

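### The documents contradict each other on follow-up after rescue surgery, so the surgery component of the treatment-policy analysis (Supplementary 1) has no securely planned post-surgery scores

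*Protocol*

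**What the plan says.** Protocol 3.7.13, on surgery during the treatment period, ends study treatment and then states: "all procedures/assessments for the ET and EOTP visits will be completed prior to the surgery. The participant will be discontinued from the study". SAP 3.1.4.9 carries the same rule: "The participant will be discontinued from the study". The list of surgery types in both places includes functional endoscopic sinus surgery, so the rule covers the ESS cases named in the estimand.

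Protocol 3.5.8 treats the same situation differently. Its illustration of a reason for an early treatment termination visit is "for example, needing sinonasal surgery as rescue treatment", and it goes on: "ET participants are encouraged to continue completing ePRO assessments through Week 24". SAP 3.1.8.3 adds, for early treatment discontinuation in general: "Data collected after treatment discontinuation will be included in the analysis". Protocol 3.5.10 also asks people withdrawn from study treatment to come back for end-of-treatment and safety follow-up visits.

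SAP 3.4.1.3 lists "Supplementary 1: Treatment policy strategy for the use of SCS for any indication or ESS". SAP Appendix C records this as new in Version 2.0 ("Added sensitivity analysis with a treatment policy for ICE of SCS use and ESS") and attributes it to regulator feedback. For corticosteroid rescue, Protocol 3.7.12 is clear: "The participant should continue with the study treatment and follow-up visits per protocol".

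**The concern.** A treatment-policy strategy uses the scores a participant reports whether or not the event has happened. For ESS it therefore needs 3CS scores from after the operation. The rule written specifically for surgery ends study participation at that point, so none is scheduled. The more general rule would allow such scores, but only by encouragement. Sites may read the two sections differently, and any post-surgery scores that do arrive would come from a self-selected subset.

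At stake is the meaning of one supplementary analysis. Supplementary 2 keeps the composite rule for ESS, and so does the per-protocol repeat of the primary model. Supplementary 1 is thus the only listed analysis that relaxes the composite for surgical cases. If their scores are modelled rather than observed, that component is closer to a hypothetical-strategy estimate than to the treatment-policy estimate that the SAP names.

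**Working it through.** **1. The plan's own figure.** SAP 2.2.4 gives 50 control and 100 LYR-210 participants, effect size 0.63, mean difference 1.31 and power 0.95; SAP 3.1.6 gives a two-sided 0.05 level. The implied SD is 1.31/0.63 = 2.08. With the normal approximation, 0.63/√(1/50 + 1/100) = 3.64, and 3.64 − 1.96 = 1.68, so power is 0.953 (0.951 by noncentral t). The stated figure reproduces. The point does not rest on it; 1.31 serves only as a yardstick.

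**2. Which analyses need which scores.**

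| Analysis | Scores after corticosteroid rescue | Scores after ESS |
|---|---|---|
| Primary (SAP Table 5) | replaced by worst observed post-baseline score | replaced likewise |
| Supplementary 2 | needed for non-CRS use only; follow-up continues | replaced by worst post-baseline score |
| Supplementary 1 | needed; follow-up continues | needed; not planned under 3.7.13, only encouraged under 3.5.8 |

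Only the last cell is in doubt.

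**3. What would fill it.** SAP 3.4.1.1 handles missing scores through the MMRM under missing at random. The multiple-imputation and tipping-point analyses in SAP 3.4.1.2 deal with scores missing under the primary estimand, where post-ESS scores are replaced and so are not missing. SAP 3.1.8.3 sets post-rescue scores aside, which is the composite handling. No section says what Supplementary 1 does when a post-ESS score is absent.

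**4. Timing.** The end-of-treatment-phase visit falls 25 to 31 days after the ET visit (Protocol 3.5.8) and must precede surgery (3.7.13). The Week 24 window for 3CS is Days 148 to 210 (SAP Table 1a). Since 148 − 25 = 123 and 148 − 31 = 117, an ET visit from Day 123 up to the scheduled Week 20 visit puts that later visit inside the window; from Day 117 to Day 122 it may. Those participants can have a Week 24 score, but it was recorded before surgery. With an earlier ET visit and no later ePRO, there may be no Week 24 score at all.

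**5. Size (illustration; the documents give no surgery rate).** Let fC and fL be the proportions in the control and LYR-210 arms with surgery and no later score. Let g be the gap between the true post-surgery score and the one implied under missing at random, taken as equal in both arms. The arm difference shifts by g × (fC − fL):

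| fC, fL | g = 1 | g = 2 | g = 3 |
|---|---|---|---|
| 2%, 2% | 0 | 0 | 0 |
| 5%, 2% | 0.03 (2.3%) | 0.06 (4.6%) | 0.09 (6.9%) |
| 10%, 5% | 0.05 (3.8%) | 0.10 (7.6%) | 0.15 (11.5%) |
| 10%, 2% | 0.08 (6.1%) | 0.16 (12.2%) | 0.24 (18.3%) |

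Percentages are of 1.31. The extreme row is 0.10 × 50 = 5 control and 0.02 × 100 = 2 LYR-210 participants.

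**6. Precision.** If 2%, 5% or 10% of the 150 (3, 7.5 or 15 participants) had no later score, simple complete-case power at effect size 0.63 would be 0.950, 0.944 or 0.932. Lost power is minor; the issue is what is being estimated.

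**The case against.** A reader might infer from 3.7.13 alone that Supplementary 1 will have no post-surgery scores whatever. The documents do not establish that. Protocol 3.5.8 names surgery as an ET example and encourages continued ePRO, and SAP 3.1.2.1 includes all follow-up data for participants who stop treatment early. Collection is contradictory and at best voluntary; it is not settled as absent.

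A reader might also infer that Supplementary 1 cannot test the composite primary result. That too goes further than the text allows. The analysis covers corticosteroid use as well, where follow-up continues, so it still tests that part of the composite. No confirmatory test depends on post-ESS scores.

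The timing argument has some force: for later surgery, a score in the Week 24 window may exist and the model need not extrapolate. It narrows the missing-data gap but does not supply a score taken after the operation.

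On size, surgical cases may be very few. An error in one arm's mean must not be read as an error in the treatment difference. For example, 5% of an arm with a 2-point miss moves that arm by 0.10, but the same rate and miss in the other arm cancel it.

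**Conclusion.** The point holds as an inconsistency with a limited analytic consequence. Protocol 3.7.13 and SAP 3.1.4.9 cannot both stand beside Protocol 3.5.8. While the surgery-specific rule applies, the ESS component of Supplementary 1 rests on missing-at-random extrapolation or on volunteered scores. The possible shift in the Supplementary 1 arm difference is 0 to 0.24 points, or 0% to 18% of 1.31. That range rests on assumed surgery rates (2% in both arms up to 10% control against 2% LYR-210) and an assumed miss of 1 to 3 points that is the same in both arms. Unequal misses would prevent exact cancellation even at equal rates. The primary composite estimand, Supplementary 2 and the corticosteroid component of Supplementary 1 are not affected.

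**What to change.** Reconcile Protocol 3.7.13 and SAP 3.1.4.9 with Protocol 3.5.8 so that the end of study treatment at surgery is separated from the end of data collection. Remote daily 4CS and scheduled SNOT-22 ePRO should then continue through Week 24. SNOT-22 belongs here because SAP 3.4.2 applies the primary endpoint's estimand attributes and methods to the SNOT-22 key secondary endpoint. Both documents need the change: editing the protocol alone would leave the SAP sentence in conflict, and 3.5.8 as written only encourages ePRO.

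An amendment cannot recover scores already missed. For participants it reaches too late, the SAP should state before the Week 24 database lock how missing post-ESS scores are handled in Supplementary 1, and the number of such participants should be reported by arm.

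The cost is a short protocol and SAP amendment and some questionnaire burden for the few participants who have surgery, using an ePRO system already in place. Decisions about surgery and the primary analysis are unchanged.

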3.7.14 Sinus CT scoring

Opacification of the ethmoid sinuses will be assessed using CT images. Two scoring methodologies will be employed to assess sinus opacification – Zinreich modified Lund-Mackay and 3-D volumetric analysis. The Zinreich modified Lund-Mackay scoring system uses a 0-5 scale for scoring each sinus. ¹⁸ The scoring is based on the percentage of sinus opacification as follows: 0 = 0%, 1 = 1% to 25%, 2 = 26% to 50%, 3 = 51% to 75%, 4 = 76% to 99%, and 5 = 100% or completely occluded. The left and right sides are graded, and the sum is the total score out of maximum of 20. 3-D volumetric scoring will involve evaluations of each slice of 3-D coronal CT sequences and summing of all the slices to create a volumetric score ranging from 0% to 100%. Sinus CT opacification scoring will be performed by

3.7.16 Physical examination

A limited physical examination including a careful assessment of the head, eyes, ears, nose and throat will be performed during Screening (**Appendix 14.1**). Height (cm), weight (kg) and body mass index (BMI) will be measured at Screening.

3.7.17 Vital signs

Vital sign measurements will include seated blood pressure (systolic and diastolic, mm Hg), and pulse rate (beats per minute), body temperature (°C) tested per local practice, and respiration rate (breaths per minute). All measurements will be obtained after the participant has been resting for at least 5 minutes.

3.7.18 Ocular examination

Ophthalmologic assessments will include measurement of corrected VA, IOP, and a slit-lamp examination of the anterior segment of the eyes to identify new or worsening cataract development. The cataract assessment will be conducted according to the Simplified Cataract Grading System authored by the World Health Organization Cataract Grading Group.¹⁹ Participants will be dilated with mydriatics following the WHO guidance for cataract assessment. IOP may be measured using Goldmann applanation tonometer, non-contact tonometer, or tonopen; however, it is recommended that the same method be used for consistency across serial assessments on a given participant. A clinically significant increase of IOP is defined as IOP in 1 or both eyes >23 mm Hg or an increase of IOP from baseline in 1 or both eyes ≥10 mm Hg. Assessments will be conducted by an ophthalmologist/optometrist who is blinded to the participant's treatment assignment.

